## **Objective**

We intend to demonstrate the feasibility of using a nasal endoscope to perform intraoperative angiography of surgical field, with the goals to evaluate anatomical landmarks and tumor characteristics during skull base surgery and publish a technical note.

## **Background and Rationale**

The expanded endoscopic endonasal approach (EEA) to the cranial base is increasingly being utilized to address a variety of cranial base pathologies. The more severe complications and morbidities associated with EEA are related to vascular and cranial nerve injury.

The sphenoid sinus is the center and starting point for all the expanded EEA to the ventral skull base. Skull base surgeons rely on anatomical landmarks and neuro-navigation to perform a safe procedure. However, sphenoid sinus pneumatization may vary and anatomical landmarks may not be readily identifiable. In addition, surgeons may not rely exclusively on neuro-navigation since it is not always accurate and precise.

Originally FDA approved for human use in 1959, indocyanine green (ICG) is a tricarboyanine dye with near-infrared fluorescence that has been routinely used in a variety of cerebrovascular procedures since 1972 for real-time noninvasive intraoperative angiography with a multiple-decades-long safety history. It is administered as an intravenous bolus, typically in a dose of 25 milligrams dissolved in 10 milliliters of sterile water. It binds to large plasma proteins within 2 seconds and remains intravascular. ICG is metabolized exclusively by the liver with a plasma half-life of 150 seconds and is excreted

in bile. Angiography is typically most useful approximately 45 seconds after ICG administration in distinct arterial, capillary, and venous phases.

There are only a few reports in the literature describing the use of ICG and the Karl Storz nasal endoscope in EEA for benign ventral skull base lesions. Litvack et al. described the intraoperative use of ICG to successfully differentiate relatively avascular tumor from the capillary-rich normal pituitary gland as well as relatively hypervascular regions of dural invasion without complication. Hide et al. that the real-time observation of the blood supply to the optic nerves and pituitary helps to predict the preservation of their function. Inoue et al. used preoperative 3D-CT and MRI fusion models with intraoperative ICG endoscopy and concluded that the technique allowed distinct visualization of vital structures in cases where tumors had extensively infiltrated the sphenoidal sinus. Additionally, the ICG endoscope was a useful real-time monitoring tool for ETSS.

There are no other reports of ICG use in any EEA approaches to the cranial base, nor are there any reports of ICG use to characterize the tumor vascularization and its relationship to optic nerves and arteries.

The usefulness of the intraoperative ICG in cranial nerve preservation was recently studied in microscopic lateral skull base approaches. The authors concluded that the course of the facial nerve can be confirmed during mastoidectomy, which reduces the possibility of iatrogenic facial nerve dysfunction. This fluorescence technique is especially helpful in establishing confidence and shortening the learning curve for beginners at mastoidectomies. We believe that the same strategy can be useful to identify the optic nerves during expanded EEA.

## **Proposal**

Based on the positive experience of our Pilot study where ICG accurately demonstrated visualization of perfusion of the pedicled flap posterior nasal arteries and mucosal flap during endoscopic endonasal approaches, we now propose a study in which we will administer ICG during routine EEA for cranial base pathologies in which optic canal decompression, intradural tumor dissection, or dissection of tumor around the internal carotid artery will be necessary.

We anticipate needing no more than thirty-five patients to obtain the necessary information and will either seek further IRB approval or terminate this feasibility study if the necessary information cannot be obtained by the thirty-fifth patient. All surgeries will be performed in a team with [name] (Neurological Surgery) and either [name] (Otolaryngology) or [name] (Otolaryngology). We will use the Storz nasal endoscope, which is already purchased and routinely used at The Ohio State University (OSU), modified as described by Litvack *et al.* to visualize the proposed real-time angiograms. These modifications include a custom xenon light source that produces both the standard white light as well as near-infrared (690-780 nm wavelength) light and a selectable near-infrared filter for the nasal endoscope, both of which will be provided by

Karl Storz free of charge. We intend to administer ICG, which is already widely used during open neurosurgical procedures, to identify anatomical landmarks (such as vascular structures leading to the optic canal and internal carotid arteries) and tumor characteristics (such as tumor vascularization, tissue differentiation, and vessel encasement) during skull base surgery at different stages of endonasal cranial base surgery and tumor dissection: before intradural dissection and during tumor dissection.

### **Eligibility**

All adult patients selected to undergo an EEA for cranial base pathology that will require any of the following will be eligible for the study: optic canal decompression, intradural tumor dissection, dissection of tumor around the internal carotid artery.

Exclusion criteria will include patient age less than 18 years; history of sulfa, iodide, or penicillin allergy; previous anaphylactic reaction to ICG; women currently pregnant or nursing. Patients of child bearing potential are routinely screened for pregnancy before the surgery using urinary or blood beta-HCG test.

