### **Management of Adverse Experiences**

#### 1. Adverse Events

##### 1.1. Adverse Event Definition

An adverse event (AE) will be considered any undesirable sign, symptom or medical condition considered related to the intervention. Medical condition/diseases present before starting the intervention will be considered AEs only if they worsen after starting the study and that worsening is considered related to the study intervention. An AE is also any undesirable and unintended effect of research occurring in human subjects as a result of the collection of identifiable private information under the research. AEs will be recorded up to the day of the final follow-up visit, and if still present, they will be recorded as “ongoing” at the end of the study. The occurrence of AEs should be sought by non-directive questioning of the patient at each visit during the study. AEs also may be detected when they are volunteered by the patient during or between visits.

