### **Risk and Benefit Assessment**

Per the 2006 FDA label for ICG, the only listed risks of ICG administration are urticarial or anaphylactic reactions, which are rare. ICG contains sodium iodide, so caution is recommended in patients with a history of iodide allergy. Per this FDA label, “There are no data available describing the signs, symptoms, or laboratory findings accompanying overdose. The LD 50 after I.V. administration ranges between 60 and 80 mg/kg in mice, 50 and 70 mg/kg in rats and 50 and 80 mg/kg in rabbits.” The FDA arbitrarily suggests a maximum dose of 2mg/kg for human use, and this would be our dosage maximum. The main risk to our study population

would be a small increase in operative time under general anesthesia, which we estimate at an additional 15 minutes. Litvack *et al.* estimated that ICG angiography during their pituitary surgeries required an extra 15-20 minutes of operative time under general anesthesia, which supports our estimation.

The benefits to our study will be visualization of important structures that may be encased by the tumor to avoid injury including the optic nerves, the internal carotids and minor feeding vessels. Also, determination of any residual tumor that may be left during tumor dissection helps prevent or recurrence of the tumor, which will overall decrease the morbidity of these kind of surgeries. We feel that the benefits to the study population markedly outweigh the risks.

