## **Data Collection**

Specifically, patient demographic/clinical information to be included in this feasibility study will include:

- a. Age
- b. Gender
- c. Race
- d. Vital Signs
- e. Diagnosis
- f. Duration of Disease
- g. Brief Medical History
- h. Description of Surgical Approach
- i. Description and Images of Intraoperative Angiography

Medical imaging data to be presented will include pre- and post-operative CT and MR studies in addition to intraoperative angiography and intraoperative endoscopic images of the surgical site.

If, during the course of the procedure, the operator determines that it would be in patient's best interest to prematurely abort the procedure due to unforeseen events, it will be under the discretion of the PI to use the data from the prematurely aborted procedure. If patient has a second procedure after the first procedure was prematurely aborted, it is up to the PI discretion to re-dose patient with the ICG dye and complete the study procedures and collect study data from the second procedure. The PI may decide whether to use the data from the first procedure in this circumstance. ICG dye half-life is 3-4 minutes and does not pose a threat of overdosing.

In summary, this novel technique for performing real-time endoscopic intranasal angiography could substantially improve the safety of surgery by precisely locating the optic canal and internal carotid arteries; by providing additional information on tumor characteristics such as vascularization and vessel encasement.

This information may prompt further surgical action to avoid the complications associated with optic canal decompression, dissection near the internal carotid and tumor dissection. Presentation of this feasibility study in the literature will likely lead to wide acceptance and implementation of this technique due to the highly useful information it will yield as well as its high degree of feasibility, as institutions performing EEA procedures already possess the materials necessary to perform it.

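### A prior reaction to ICG bars entry only if it was anaphylactic, although the protocol also lists urticaria as an ICG risk and bars other allergies with no severity limit

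*Protocol*

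**What the plan says.** Allergy-related exclusions stand in one sentence of the protocol's Eligibility section: "history of sulfa, iodide, or penicillin allergy; previous anaphylactic reaction to ICG". The first three conditions have no qualifier. The fourth is limited to anaphylaxis.

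The Risk and Benefit Assessment, reporting the product label, states that "the only listed risks of ICG administration are urticarial or anaphylactic reactions, which are rare". On iodide it says that "ICG contains sodium iodide, so caution is recommended in patients with a history of iodide allergy".

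Three other places bear on the point:

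- The adverse event definition (section 1.1 under Management of Adverse Experiences) covers "any undesirable sign, symptom or medical condition considered related to the intervention".
- Data Collection provides that, after an aborted first procedure, "it is up to the PI discretion to re-dose patient with the ICG dye".
- The Proposal sets the size of the study: "We anticipate needing no more than thirty-five patients to obtain the necessary information".

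**The concern.** Eligibility and the risk section do not line up. The protocol recognises urticaria as one of two reactions the dye can cause, but a patient known to have had it from this dye passes the exclusion list. In the same sentence, an allergy of any degree to a component of the dye, or to two drug classes that the risk section does not mention, is enough to exclude. One would expect the rule to be at least as strict for the study agent as for an indirect marker of sensitivity to it.

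What is at stake is patient safety at entry, on a small scale. The wording has no bearing on sample size, error rates or any estimate.

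**Working it through.** The protocol gives no figure on this point, so the check is a comparison of text.

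**Step 1: set the entry rule beside the risk statement.**

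| History at screening | Severity limit in Eligibility | Mention in Risk and Benefit Assessment | Result as written |
|---|---|---|---|
| Sulfa allergy | None | None | Excluded |
| Penicillin allergy | None | None | Excluded |
| Iodide allergy | None | Caution only | Excluded |
| Anaphylaxis to ICG | Meets the limit | Listed risk | Excluded |
| Urticaria from ICG | Falls below the limit | Listed risk | Not excluded |

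**Step 2: count.**

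- ICG reaction types listed as risks: 2 (urticarial, anaphylactic). Excluded by name when previously experienced: 1. Coverage is 1 of 2.
- Allergy-type exclusions: 4 (sulfa, iodide, penicillin, ICG). With a severity threshold: 1, the ICG item.

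**Step 3: look for another rule that closes the gap.**

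- The iodide exclusion catches an earlier ICG urticaria only if that reaction was recorded as an iodide allergy. The protocol does not say that it should be.
- The adverse event definition captures a reaction after a study dose. It does not decide who receives one.
- The re-dosing provision in Data Collection attaches no condition about a reaction to the first dose. If the exclusion list were applied again at that point, it would stop only a patient whose first reaction was anaphylactic.
- No other section excludes a patient with a previous non-anaphylactic reaction to ICG, or sets precautions for one.

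**Step 4: size.** The number affected cannot be calculated. The protocol describes the reactions only as rare and gives no rate for earlier ICG exposure among these patients. Both conditions must hold in the same person, and the planned maximum is 35, so few or none are expected.

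**The case against.** The strongest reply is that there is no contradiction. A list of risks does not oblige a protocol to exclude everyone who has had each of them, and barring the severe reaction while accepting the mild one can be a deliberate choice. The documents do not say that earlier urticaria predicts a worse reaction on re-exposure, so the safety benefit of a wider rule is not shown there. The broad sulfa and penicillin exclusions have no stated rationale and may simply be over-cautious; they do not prove that the ICG item is too loose. The phrase introducing the exclusions can also be read as non-exhaustive, and the iodide item will catch some of these patients.

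Part of this stands. The documents do not quantify a benefit, the absence of a severity limit for the other allergies is read from the absence of a qualifier, and the effect is very small. The reading as a deliberate choice is harder to sustain. For iodide the protocol goes further than the caution it reports and excludes outright, because the dye contains it. A protocol that reasons this way about a component has no evident ground for admitting a patient with a known hypersensitivity reaction to the whole product, and it offers none. A non-exhaustive list is not much help either: the sentence addresses ICG reactions specifically and restricts them to anaphylaxis, so a person screening from it would reasonably take urticaria to be acceptable.

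**Conclusion.** The concern holds, as a minor point worth considering. The exclusion "previous anaphylactic reaction to ICG" is narrower than the ICG risks the protocol itself lists, and narrower than "history of sulfa, iodide, or penicillin allergy" in the same sentence. A patient with earlier urticaria from ICG is eligible as the text stands, with the one exception of a reaction recorded as iodide allergy.

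This rests on two readings: that an exclusion without a qualifier applies at any severity, and that the exclusion list is applied as written. It does not assume that earlier urticaria leads to a more severe reaction. The gap concerns entry only, since urticaria related to a study dose would still be recorded as an adverse event. Neither the feasibility objective nor any estimate is affected.

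**What to change.** In Eligibility, replace the ICG item with: *any previous hypersensitivity reaction to ICG, including urticaria*.

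This is one changed phrase, which can go into the next amendment. The cost is that a very few patients with earlier ICG urticaria would not be enrolled. Because the dye is added to surgery that is planned anyway, nothing in the protocol suggests that such a patient would lose the operation.

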### **Management of Adverse Experiences**

#### 1. Adverse Events

##### 1.1. Adverse Event Definition

An adverse event (AE) will be considered any undesirable sign, symptom or medical condition considered related to the intervention. Medical condition/diseases present before starting the intervention will be considered AEs only if they worsen after starting the study and that worsening is considered related to the study intervention. An AE is also any undesirable and unintended effect of research occurring in human subjects as a result of the collection of identifiable private information under the research. AEs will be recorded up to the day of the final follow-up visit, and if still present, they will be recorded as “ongoing” at the end of the study. The occurrence of AEs should be sought by non-directive questioning of the patient at each visit during the study. AEs also may be detected when they are volunteered by the patient during or between visits.

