## **Human Subjects**

### 1. Institutional Review Board (IRB) Review and Informed Consent

This protocol and the informed consent document and any subsequent modifications will be reviewed and approved by the IRB or ethics committee responsible for oversight of the study. A signed consent form will be obtained from the subject. The consent form will describe the purpose of the study, the procedures to be followed, and the risks and benefits of participation, and the rights of the participant. A copy of the consent form will be given to the subject and this fact will be documented in the subject's record.

The Principal Investigator or the Study Coordinator will be responsible for submitting any changes to the project to the IRB for approval prior to implementation of the changes. The study will also be submitted for continuing review by the IRB at periods determined by the IRB, at least annually, for the duration of the study.

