### 2. Subject Confidentiality

Subject data records will be identified by a study specific identification number. All subject records will be kept in a locked file cabinet. All computer entry and networking programs will be done using study specific identification number only. Clinical information will not be released without written permission of the subject, except as necessary for monitoring by IRB, the FDA, the OHRP, the sponsor, or the sponsor's designee.

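### The adverse event definition requires relatedness to an undefined intervention, so an injury attributed to the operation alone need not enter the study's AE record

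*Protocol*

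**What the plan says.** The protocol's section 1.1, Adverse Event Definition, opens with the rule that "An adverse event (AE) will be considered any undesirable sign, symptom or medical condition considered related to the intervention". For conditions present beforehand it asks for two things: that they worsen, and "that worsening is considered related to the study intervention". The one extension covers harm from collecting identifiable information. The section goes on to say that AEs are recorded up to the final follow-up visit and sought by non-directive questioning. It does not say what the intervention consists of, or who decides relatedness.

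The Proposal describes the study as a plan to "administer ICG during routine EEA for cranial base pathologies", with the dye given before intradural dissection and during tumor dissection. On size it says "We anticipate needing no more than thirty-five patients to obtain the necessary information". Background and Rationale names the main harms of the operation: "The more severe complications and morbidities associated with EEA are related to vascular and cranial nerve injury". Risk and Benefit Assessment gives, as the expected benefit, seeing important structures "to avoid injury including the optic nerves, the internal carotids and minor feeding vessels", and the closing text of Data Collection expresses the hope that the technique will make surgery safer.

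**The concern.** Relatedness is usually recorded about an event after the event has been written down. Here it decides whether the event is an AE at all. A judgement made case by case, by someone who knows that the dye was given, then determines what the safety record contains. An event screened out in this way is not on the AE record to be reconsidered later or compared with similar events in other patients.

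This matters most for carotid and optic nerve injury. The images are meant to inform dissection around these structures, so it can be hard to say whether an injury came from the operation or from what the surgeon saw on the angiogram. What is at stake is the completeness of the safety listing. The feasibility result itself is not at stake.

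**Working it through.** No arithmetic applies: the protocol gives no event rate, and the point concerns the wording of a rule. The check is to apply the definition to the kinds of event that could occur.

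**Meaning of the intervention.** The term is undefined. Section 1.1 uses the phrase study intervention when it deals with pre-existing disease, and the Proposal calls the operation routine and presents ICG as what the study adds. The narrower reading, ICG angiography, is therefore the natural one. A broader reading that takes in the whole operation is possible.

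**Applying the rule on the narrower reading.**

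1. An urticarial or anaphylactic reaction considered due to the dye is an AE.
2. An event considered due to the added time under anesthesia (estimated at 15 minutes in Risk and Benefit Assessment) is an AE.
3. A carotid or optic nerve injury judged to follow from dissection guided, or misled, by the ICG image is an AE.
4. The same injury attributed to the operation alone is not an AE and need not be recorded as one.

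Cases 3 and 4 can be the same injury in the same patient. Only the attribution differs.

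**Looking for another rule that would capture case 4.**

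- Non-directive questioning and recording to final follow-up apply to AEs as already defined, so they do not lift the condition.
- The extension for harm from collecting information does not reach surgical injury.
- Data Collection includes post-operative CT and MR and intraoperative endoscopic images. These may show some injuries, but nothing requires an injury seen there to be logged as an event.
- The human-subjects section says that "The study will also be submitted for continuing review by the IRB at periods determined by the IRB, at least annually". The confidentiality section bars release of clinical information without written permission "except as necessary for monitoring by IRB, the FDA, the OHRP, the sponsor" or the sponsor's designee. Oversight and access do not create an AE entry.

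No sentence in the protocol requires an event judged unrelated to be recorded.

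**The case against.** The strongest reply is that little depends on this. The objective is feasibility and a technical note, no complication rate is planned, and without a control group even a complete list of injuries could not show that surgery had become safer. That stands, and it limits the point to the completeness of the AE record.

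A second reply is that the injuries most informative about the technique are already covered, because an injury thought to follow from ICG-guided dissection counts as related. That also stands as a reading of the rule. A reader might infer that every injury from the operation escapes the record, and the text does not support this. What remains is that inclusion depends on an attribution that is difficult for these very injuries.

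A third reply is that the intervention might include the operation, which would bring surgical injuries in. The wording permits that reading but does not favor it. If it was intended, the protocol needs to say so.

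A reader might also take the lettered list in Data Collection, which has no item for complications, as proof that injuries go uncaptured. It is weak support. The list also omits AEs that plainly meet the definition, and these have their own recording instruction in section 1.1.

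**Conclusion.** The point holds as a minor defect of definition. Section 1.1 makes relatedness to an undefined intervention a condition of being an AE, both for new events and for worsening of existing disease. Followed exactly, it gives a record filtered by a prior causality judgement, and a vascular or cranial nerve injury attributed to the operation alone need not appear in it.

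This rests on one assumption, that the intervention means ICG angiography and not the whole operation. The protocol's language favors that reading without stating it. The wording of the rule is certain; its consequence for surgical injuries is less so.

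No magnitude can be derived. A reader might be tempted to express one omitted patient as a share of the 35-patient ceiling, but that would say nothing about how often omission would occur or what effect it would have. Nor do the documents support saying that the feasibility aim is compromised or that a planned safety estimate is biased, since the protocol plans none.

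**What to change.** Make three changes in section 1.1.

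1. Define an AE as any untoward sign, symptom or condition that arises or worsens between the start of the study operation and the final follow-up visit, whether or not it is considered related. Flag whether onset was before or after the first ICG injection. Opening the window at the start of the operation keeps injuries of the approach phase in view, and the flag separates those that cannot be due to the dye.
2. Define the intervention as ICG angiography, including the operative time it adds.
3. Record relatedness to the intervention and relatedness to the surgery as two separate fields, completed by a stated role within the existing team.

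The changes affect recording only. They cost a reworded definition, two relatedness fields and an onset flag, and slightly more abstraction from records for at most 35 patients. The downside is a longer event list, most of it surgical; the relatedness fields allow it to be sorted.
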